# 5.2 Prenatal Sequencing Group Only

The primary and secondary outcomes for the sequencing variants are descriptive and will be reported as the observed proportion (frequency) with 95% confidence intervals. Exact confidence intervals will be reported as appropriate. Sequencing findings include variants or no variants (negative). Variants are further classified as pathogenic, likely pathogenic, or VUS. VUS is further categorized by whether the variants are in genes related to the fetal phenotype or known to cause severe childhood disease, or in a gene of uncertain significance (GUS). Sequencing findings will be reported overall, by single vs. multiple anomalies, by organ system (abdominal wall, CNS, face/ear, effusion, intrauterine fetal growth, GI tract, genitalia, heart, neck, renal tract, skeletal, spine, thorax), and by key demographics including maternal age, race/ethnicity and fetal sex. Pearson's chi-square or Fisher's Exact test for categorical variables and

Mann-Whitney U test for continuous outcomes will be used to assess associations by variant classification.

For each variant meeting the primary outcome definition (pathogenic, likely pathogenic, and uncertain genomic variants), the type of test that would identify the variant (WGS only, WES) will be determined centrally and used to report the incremental number of pathogenic, likely pathogenic, and VUS variants identified by WGS compared with WES.

Change in management decisions attributable to sequencing results are descriptive and will be reported as the frequency with 95% confidence intervals overall and by variant classification.

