While WGS results may illuminate the situation when a well-known genetic condition is diagnosed, there are challenges in counseling for some of the newer genetic conditions for which less data are available. In CMA, variants of uncertain clinical significance (VUS) and those associated with variable expressivity occur in a proportion of cases with structural anomalies (5.3%) and require extensive genetic counseling. Other counseling issues include the identification of adult onset disorders of both the fetus and parent. To understand attitudes and unmet needs in the adoption of CMA testing semi-structured interviews with parents and counselors were performed to evaluate pre-test counseling, reporting of results, and assessing patient and provider experiences. From the patient perspective, 5 key themes were identified 1) accepting CMA testing was an easy decision to make as patients would obtain additional information on their baby's health at no additional cost, 2) patients were blindsided by the results in cases where they initially received a normal karyotype result followed by an abnormal CMA, 3) abnormal results left patients shocked, anxious, confused and overwhelmed, 4) patients needed support to manage, understand and act on the microarray results, and 5) uncertain findings were felt to be toxic knowledge and patients wished they did not receive the results. It is anticipated that the needs for prenatal sequencing will be similar to those of prenatal CMA and that prior studies will inform the educational and support materials developed for prenatal sequencing.

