# 4.10 Study Outcome Measures and Ascertainment

#### 4.10.1 Primary Outcome

- 1. Pathogenic, likely pathogenic, or VUS variants identified by sequencing and deemed reportable by the Variant Adjudication Committee
- 2. Maternal hospital charges between time of presentation to hospital for delivery to discharge, and neonatal hospital charges between delivery and infant discharge or death

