#### 4.10.3 Secondary Outcomes (Prenatal sequencing only)

- 10. Apparent prenatal phenotypic expansion from currently defined pediatric phenotypes
- 11. Variants of uncertain significance (VUS) that have not yet been associated with this disease phenotype
- 12. VUS subclassified as compelling variants in novel genes that are not yet disease associated (genes of uncertain clinical significance; GUS)
- 13. Pathogenic, likely pathogenic and VUS variants identified by sequencing (coding and non-coding regions) compared with coding regions only (digital WES)
- 14. Pathogenic, likely pathogenic and VUS variants identified by analysis of a proband alone compared to a proband-parent trio
- 15. Change in management decisions attributable to genomic results defined as changes to the patient's treatment plan or changes to the counseling of the patient/family regarding the immediate or long-term medical management
- 16. Accuracy of parental understanding of genetic test results
- 17. Educational/counseling and social support needs of the mother and father
- 18. Changes in classification of sequencing variants over time
- 19. Turnaround time of sequencing components and how it changes over time.

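### The WGS-over-WES increment counts variants rather than diagnosed fetuses, and the proband-versus-trio comparison has no defined unit

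*Combined protocol and SAP*

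**What the plan says.** Section 5.2 (same text in protocol versions 1.0 and 1.8) handles WGS versus WES in one sentence. It covers variants that meet the primary outcome definition, which section 4.10.1 gives as "Pathogenic, likely pathogenic, or VUS variants identified by sequencing and deemed reportable by the Variant Adjudication Committee". For each, "the type of test that would identify the variant (WGS only, WES) will be determined centrally", and the label is "used to report the incremental number of pathogenic, likely pathogenic, and VUS variants identified by WGS compared with WES". Outcome 13 in section 4.10.3 is the matching secondary outcome; there WES is digital, meaning the coding part of the same genome data.

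Outcome 14 reads "Pathogenic, likely pathogenic and VUS variants identified by analysis of a proband alone compared to a proband-parent trio". Section 5.2 gives it no method of its own. It falls under the opening rule, "The primary and secondary outcomes for the sequencing variants are descriptive and will be reported as" observed proportions with 95% confidence intervals, exact where appropriate. That rule names no denominator and does not say how to treat a fetus with several variants.

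Other sections set out the purpose. Aim 1a (section 1.2) asks for relative yield and names uncertain variants as part of it. Section 2.3 says that analysing coding and then non-coding regions allows differences in diagnostic yield to be compared. Section 5.1 plans on 22 diagnoses in 234 trios (9.4%) and 750 sequenced pregnancies.

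**The concern.** Diagnostic yield is a property of the fetus: the analysis gives a diagnosis or it does not. A number of variants is a different quantity. It rises when one diagnosis needs two alleles, and when an uncertain finding is added to a case already solved. The WES/WGS-only label records which test detects a variant, not which test makes the diagnosis possible.

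What is at stake is the answer to Aim 1a and section 2.3. A reader of the final report will want to know how many more fetuses were diagnosed because the whole genome was read, or because the parents were sequenced. The planned figure does not give that number. Counting VUS alongside diagnoses also sits badly with the background in section 2.2.4, where interviews about microarray testing found that "uncertain findings were felt to be toxic knowledge and patients wished they did not receive the results".

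**Working it through.** **1. The plan's own figure, and the unit behind it.** Inputs from section 5.1: n = 750, p = 22/234 = 9.4%, half-width 2.3%, probability 93%. With X ~ Binomial(750, 0.094), the probability that the exact (Clopper-Pearson) 95% interval has half-width of at most 0.023 is 0.931. This reproduces the stated 93%. The calculation takes one yes/no result per fetus; a count of variants is not binomial in 750.

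**2. What the section 5.2 labels record, by type of fetus.**

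| Fetus | Labelled WES | Labelled WGS only | Diagnosed from coding alone | Diagnosis requires WGS |
|---|---|---|---|---|
| A. One coding P/LP variant | 1 | 0 | yes | no |
| B. Two coding alleles, one recessive diagnosis | 2 | 0 | yes | no |
| C. Coding diagnosis plus a reportable non-coding VUS | 1 | 1 | yes | no |
| D. Coding allele plus non-coding second hit | 1 | 1 | no | yes |
| E. Two non-coding alleles, one recessive diagnosis | 0 | 2 | no | yes |
| F. Reportable non-coding VUS only | 0 | 1 | no | no |

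C and D give the same counts, but only D is a diagnosis gained by WGS. In D the coding allele is credited to WES although coding analysis alone would not have made the diagnosis. E adds two to the increment for one diagnosis, and B adds two to the WES total for one diagnosis. Splitting by class separates C from D if the second hit is classed P/LP, but it does not cure B or E, or the WES credit in D.

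**3. Size of the double count.** Expected diagnosed fetuses: 750 × 0.094 = 70.5. If a share r of diagnoses is compound heterozygous and the rest involve one variant, the variant total is 70.5 × (1 + r). The documents give no r, so a range is assumed:

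- r = 0: 70.5
- r = 10%: 77.6
- r = 20%: 84.6
- r = 40%: 98.7

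This is the total over both labels. The WGS-only part is inflated only by fetuses like E. A homozygous diagnosis may be logged once.

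**4. What a per-fetus increment would look like.** Exact 95% intervals for assumed numbers of fetuses whose diagnosis requires WGS:

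- 0/750: 0 to 0.5%
- 7/750 = 0.9%: 0.4 to 1.9%
- 22/750 = 2.9%: 1.8 to 4.4%

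**5. Can the weaker analysis score higher?**

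*WGS versus digital WES:* no. Every coding finding is also in the genome data, so the increment is zero or positive.

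*Proband versus trio:* possibly. Section 4.5 uses mode of inheritance in evaluating variants, and a proband-only analysis lacks the parental data for that. Assume one variant per diagnosis, 10% of diagnoses lost without parents, and reportable VUS at 0.10 per fetus (trio) and 0.15 (proband only):

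- Trio: 70.5 + 750 × 0.10 = 145.5
- Proband only: 63.45 + 750 × 0.15 = 175.95
- Proband only with VUS also at 0.10: 63.45 + 75 = 138.45, so trio leads

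Break-even is 7.05/750 = 0.009 extra VUS per fetus at 10% loss and 14.1/750 = 0.019 at 20%. These sums drop lost diagnoses from the count. If they were downgraded to reportable VUS instead, the pooled total would lose nothing and break-even would be zero.

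**The case against.** The best defence has four parts.

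- **Including VUS is the stated aim.** Aim 1a names uncertain variants, and gene discovery is one of the study's purposes. Variant counts are informative for both. This stands: VUS should not be dropped.
- **The text can be read class by class.** Section 5.2 lists the three classes separately, so a loss of P/LP findings would be visible beside a rise in VUS. This stands in part. It weakens any reversal of ranking but does not stop one recessive diagnosis counting twice.
- **Reportability filters the count.** Only variants relevant to the phenotype and deemed reportable qualify, so stray VUS would mostly be excluded. This limits the size of the problem but does not remove it, since a reportable VUS still counts as increment.
- **The outcomes are secondary and descriptive**, and section 7.1 calls the non-coding work exploratory. This stands; no test, alpha or sample size depends on it.

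Three stronger readings are tempting, and the documents do not support them. A reader might infer that WES could outscore WGS, but digital WES is nested in WGS. A reader might infer that outcome 14 is a declared variant count. Yet section 5.2's general rule is a proportion, its findings are variants or none, and section 5.1 counts participants, so the unit is undefined rather than wrong. A reader might also infer that a binomial interval on variants is planned for WGS versus WES, but section 5.2 promises only a number.

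**Conclusion.** The point holds as a modest improvement to the analysis plan. As written, the WGS-versus-WES increment does not measure the gain in diagnosed fetuses, and no per-fetus increment or interval is specified. For proband versus trio, neither a unit nor a paired method is given. A total pooled over classes could favour proband-only analysis, but only if classes are in fact pooled and unresolved proband-only VUS pass as reportable.

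The size cannot be fixed from the documents. Under an assumed compound-heterozygous share of 10–40%, the variant total exceeds the number of diagnosed fetuses by the same 10–40% (about 78–99 variants for 70.5 fetuses). The VUS rates and lost diagnoses in the proband example are also assumptions, and the ranking depends on them. The primary precision calculation reproduces and is not affected.

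**What to change.** In section 5.2 and outcomes 13 and 14, make the fetus the unit of comparison.

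- **WGS versus WES:** report the number and proportion of sequenced fetuses whose P/LP diagnosis requires WGS, including those where a coding allele needs a WGS-only second hit, with an exact 95% CI. Count a recessive diagnosis once.
- **Proband versus trio:** report the paired 2×2 table of fetuses with a P/LP diagnosis (both, trio only, proband only, neither) and the paired difference with a 95% CI.
- **VUS:** report by class and per fetus for each strategy, separately from diagnoses.
- **Variant counts:** keep them as a supplement, so that Aim 1a's uncertain variants are still covered.

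The cost is a little more analysis work. The central determination already made for each variant would need a per-fetus conclusion. The proband-only classification must be recorded for each fetus: section 6.1.1 lists mutation type, description and inheritance for form PG06A but shows no proband-only field. Sample size, alpha and power do not change.

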## 5.3 Prenatal Sequencing and Prenatal Unsequenced Groups

Clinical management including health care utilization and cost, and pregnancy and neonatal outcomes will be compared among the prenatal sequencing group and the unsequenced prenatal group (prospective and retrospective). Women whose fetus or neonate is found to have pathogenic or likely pathogenic causal findings on CMA prior to neonatal discharge will be excluded from these analyses. Twelve month postpartum outcomes will be compared only among those individuals enrolled prospectively. Initially, demographic data and severity of ultrasound findings will be compared to ensure there are no significant differences between the two study groups (prenatal sequencing and unsequenced prenatal group). If differences are found, the covariates will be adjusted for in the analyses.

Categorical variables will be reported as the number and frequency and associations assessed by the Pearson's chi-square or Fisher's Exact test. The distributions for continuous variables will be assessed for normality and transformed to fit a normal distribution if possible. Normal distributions will be reported as mean and standard deviation and compared with the t-test, and non-normal data will be reported as median and interquartile range and compared with the Mann-Whitney U test.

For each outcome, if the study groups show a significant difference, interactions will be tested and subgroup analyses conducted if the interaction is significant (p<0.05). Pre-specified subgroup analyses include maternal age, race/ethnicity, fetal sex, and type of anomaly (lethal vs non-lethal).

The amount of missing data, missing data patterns, and identification of variables associated with missingness will be explored to inform the primary and sensitivity statistical analyses. Analytic techniques used to address missing data bias will be used as appropriate. A two-sided nominal p-value less than 0.05 will indicate statistical significance.

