#### 5 Statistical Considerations

# 5.1 Power and sample size

The first primary outcome for this study is the frequency of pathogenic, likely pathogenic, or VUS genomic variants identified by sequencing among participants with a normal karyotype and CMA. The sample size is based on the incremental yield reported in a prospective study of WES performed at Columbia University in a similar population. Among 234 parent-fetus trios without CMA abnormalities, a genetic diagnosis was reported in 22 (9.4%). The precision of the estimate for a range of sample sizes and estimates is shown in Table 4. An estimate of 9.4% and sample size of 750 in the prenatal sequenced group will have a precision of 2.3% (confidence interval half-width) with a 93% probability.

Estimate	Sample size	Cl ½-width
9.0%	700	2.4%
	750	2.3%
	800	2.2%
9.4%	700	2.4%
	750	2.3%
	800	2.3%
9.8%	700	2.5%
	750	2.4%
	800	2.3%

The second primary outcome is maternal and neonatal hospital charges. The utilization of health care and cost only will include women that deliver at one of the study centers. Given that some of the recruiting centers include referrals in which the women will not deliver at the study center, power estimates assume cost will be available on 500 of the 750 in the prenatal sequencing group. Similarly, of the 350 unsequenced prenatal controls, 15% are assumed to have a pathogenic or likely pathogenic causal pre-/postnatal CMA prior to neonatal discharge or deliver elsewhere resulting in approximately 300 unsequenced prenatal controls available for analysis. The total charges for deliveries at Columbia University that required a NICU admission in 2016 and 2017 (partial year) were used to provide cost estimates. The charges follow a lognormal distribution approximately with a mean total charge of \$277,902 and standard deviation of \$389,484. Assuming 500 participants in the prenatal WGS group, and 300 unsequenced prenatal control participants, the study will have 80% power to detect a mean ratio of 0.80 (20% reduction) with an alpha=0.05 two-sided.

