#### 5.3.1 Healthcare utilization and cost

Direct medical costs include cost of all medical care for the woman and newborn during the delivery hospitalization. These costs will be estimated using health care charges associated with each of these services. Unit costs will be adjusted by health system specific cost-to-charge ratios. If cost-to-charge ratios are not available, published ratios or in rare cases Medicaid reimbursements will be used.

The effect or outcome measure for cost effectiveness will be quality-adjusted life years (QALYs). Maternal and neonatal QALYs will be estimated by applying published utility weights (1=perfect health, 0=death) from various health states to components of the conditions found by sequencing. Cost-effectiveness of prenatal sequencing will be evaluated as the incremental cost per QALY with a threshold of less than \$100,000 per QALY as cost effective. Cost benefit analysis will also be performed and be evaluated by dividing the costs of care and outcomes from the intervention by the costs of usual care. A CBA < 1 indicates that the intervention is cost saving and thereby cost beneficial.

All estimates of costs and outcomes will be reported as means with 95% confidence intervals. Sensitivity analysis will be conducted to evaluate the impact of uncertainty on the results. Varying probabilities (e.g.

baseline risk of sequencing findings, change in neonatal outcomes) and cost parameters (e.g. cost of sequencing, healthcare costs) will be used to take into account potential clinical scenarios that might deviate from the baseline estimates. One-way deterministic sensitivity analysis for individual factors will be employed and Monte Carlo simulation to assess the robustness of the findings by simultaneously sampling distributions around multiple parameters within the model and report 95% confidence ellipses and acceptability curves.

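### Section 5.3 adjusts the non-randomized group comparisons only if baseline differences are found, and does not name site, although hospital charges from several centers are a primary outcome

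*Combined protocol and SAP*

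**What the plan says.** All references are to the current protocol (version 1.8) unless stated.

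- **Baseline check (5.3).** "Initially, demographic data and severity of ultrasound findings will be compared to ensure there are no significant differences between the two study groups". Then: "If differences are found, the covariates will be adjusted for in the analyses". The tests listed next are unadjusted: chi-square or Fisher's exact, t-test, Mann-Whitney. Site appears neither in the baseline comparison nor among the subgroups.
- **Missing data (5.3).** The pattern of missing data and "identification of variables associated with missingness will be explored to inform the primary and sensitivity statistical analyses".
- **Primary outcome (4.10.1).** "Maternal hospital charges between time of presentation to hospital for delivery to discharge, and neonatal hospital charges between delivery and infant discharge or death".
- **Who is analyzed for charges (5.1).** "The utilization of health care and cost only will include women that deliver at one of the study centers". The reason given is that "some of the recruiting centers include referrals in which the women will not deliver at the study center". Costs are assumed available for 500 of 750 sequenced women. Of 350 controls, "15% are assumed to have a pathogenic or likely pathogenic causal pre-/postnatal CMA prior to neonatal discharge or deliver elsewhere", leaving about 300.
- **Cost estimation (5.3.1).** "Unit costs will be adjusted by health system specific cost-to-charge ratios". No covariate model for charges is given.
- **Psychosocial outcomes (5.3.2).** These are to be modeled with adjustment for variables thought to affect the outcome. That step does not depend on a baseline test.

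**The concern.** Confounding is built into the design. Sequenced women had invasive sampling and accepted sequencing (4.2.1). Prospective controls declined sequencing (3.2.2.1). Retrospective controls are screening-log women who did not pursue sequencing and did not actively decline enrollment (3.2.3.1, 4.2.3). In such a comparison a non-significant baseline test does not show balance, and which covariates enter should not depend on it. The rule also leaves open what counts as a difference. If none is found, a primary outcome falls to an unadjusted two-sample test.

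Site is the more important gap for charges, because charge levels, practice and case mix can all vary by hospital. Outside delivery is tied to some recruiting centers only, so restriction to study-center deliveries can change the site mix of one group more than the other. Section 9.2 also allows more sites to be added. A mix difference left out of the model would look like a saving or an excess attributable to sequencing.

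**Working it through.** **1. The plan's own power figure.** Inputs from 5.1: mean charge $277,902, SD $389,484, lognormal, 500 versus 300, ratio 0.80, two-sided 0.05.

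- CV = 389,484 / 277,902 = 1.4015
- SD of log charge = sqrt(ln(1 + 1.4015²)) = 1.0424
- SE of log ratio = 1.0424 × sqrt(1/500 + 1/300) = 0.0761
- Power = Φ(0.2231 / 0.0761 − 1.96) = 83.4%

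The plan states 80%. The plan is slightly conservative, and the point does not depend on the difference.

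**2. The conditional rule alone.** With 500 versus 300, a 0.10 SD covariate imbalance has noncentrality 0.10 / sqrt(1/500 + 1/300) = 1.37, so a two-sided 5% baseline test misses it 72% of the time. The effect on the charge comparison was simulated under the null (6,000 runs). Assumptions: each covariate is imbalanced by 0.10 SD, and together the covariates explain 30% of log-charge variance.

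| Covariates | Null ratio, gated | Type I error, gated | Type I error, always adjusted |
|---|---|---|---|
| 1 | 0.973 | 6.0% | 5.6% |
| 4, correlation 0.3 | 0.977 | 5.6% | 5.0% |
| 4, correlation 0.5 | 0.987 | 4.8% | 5.0% |
| 6, correlation 0.3 | 0.988 | 5.2% | 4.7% |
| 6, correlation 0.5 | 0.992 | 4.8% | 4.9% |

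Only a near-worst case, with four to six independent covariates all worse in controls, reaches ratios of 0.95 to 0.94 and 11-14% error.

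**3. Leaving site out.** The documents give neither site mix nor charges by site, so this step is illustrative. Assume two equal center groups, one of which takes the referrals that deliver elsewhere. Before loss, each has 375 sequenced women and 175 controls. The referral centers' share after the planned losses could be:

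- Sequenced: 250/500 = 0.50 (equal loss); 187.5/500 = 0.375 (50% kept versus 83%); 125/500 = 0.25 (33% kept versus 100%).
- Controls: 150/300 = 0.50 (even loss); 125/300 = 0.417 (all 50 lost at referral centers).

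The gaps (controls minus sequenced) are then 0, 4.2, 12.5, 16.7 or 25 points, or 8.3 points the other way if only the control loss is concentrated. With referral centers charging more by a given factor, the null ratio is factor^(−gap). Type I error is from 20,000 simulated runs.

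| Gap (points) | Null ratio, 1.25-fold | Type I error, 1.25-fold | Null ratio, 1.5-fold | Type I error, 1.5-fold |
|---|---|---|---|---|
| 0 | 1.00 | 5.0% | 1.00 | 4.8% |
| 4.2 | 0.99 | 4.9% | 0.98 | 5.2% |
| 12.5 | 0.97 | 6.4% | 0.95 | 10.0% |
| 16.7 | 0.96 | 7.7% | 0.93 | 14.1% |
| 25 | 0.95 | 11.2% | 0.90 | 26.2% |

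At 1.1-fold the ratios run from 1.00 to 0.98 and the error stays at 5-6%. At 1.25-fold, the 4.2-, 16.7- and 25-point gaps amount to 4%, 17% and 25% of the targeted log effect, for example ln(0.946)/ln(0.80) = 25%. Ratios exceed 1 if the referral centers charge less. With site in the model the ratio is 1.00 and the error 4-5%.

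Had site been in the baseline comparison, gaps of 12.5, 16.7 and 25 points would have been flagged 93%, 99.8% and over 99.9% of the time. For larger gaps, then, the omission of site matters more than the gate.

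**The case against.** **The gate is nearly harmless, and a difference will probably be found anyway.** This mostly stands. With parental choice and many baseline items, some covariate is likely to be flagged, and step 2 shows little cost in the more plausible settings. It does not help with site, which is never compared.

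**The site harm is assumed.** This stands as to size. A reader might infer from losses of one third among sequenced women and 15% among controls that site mix will differ. The documents do not support that. Both figures are planning assumptions, unchanged since version 1.0, before retrospective controls existed. The 15% mixes causal microarray results with outside delivery. Section 5.1 presents the two losses as similar, and proportional losses give no bias. The 12.5- and 25-point gaps require loss concentrated at referral centers in one group and even in the other.

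**Existing provisions already help.** In part. Severity and demographic adjustment, if triggered, would absorb some site case mix, and cost-to-charge ratios would reduce price differences. Step 3 credits neither. However, 4.10.1 defines the outcome as charges, conversion leaves practice differences in place, and the missing-data sentence could bring site in but does not commit to it.

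**A rewritten rule could do harm.** A sentence confined to charges would remove the only adjustment rule for the other 5.3 outcomes. A list with maternal age as its sole demographic would drop ethnicity and socioeconomic status, which section 2.2.4 itself links to attitudes toward prenatal testing. Adjusting for delivery site could remove part of the effect, because section 2.1 says sequencing may guide delivery plans. The wording proposed under the fix avoids all three.

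**Conclusion.** The plan makes adjustment of a non-randomized comparison depend on baseline findings and names no site term for a multicenter charge outcome. No other section supplies one. That is a clear reading of the text and should be fixed, mainly because a better rule is cheap.

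The size is modest or unknown. The conditional rule alone gives about 5-6% type I error in most settings tried. The site bias cannot be sized from the documents and may be zero. The range of 0.99 to 0.95 in the null ratio, with 5-11% false positives, rests on an assumed two-group site structure, a 1.25-fold charge difference, mix gaps of 4 to 25 points, and no credit for existing provisions. It would be wrong to conclude that the charge comparison is biased, or biased in a known direction.

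**What to change.** Keep the baseline comparison as description, reported as standardized differences. Replace "If differences are found, the covariates will be adjusted for in the analyses" with:

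> All between-group comparisons in this section will be adjusted for pre-specified covariates whatever the baseline comparisons show: recruiting site, maternal age, race/ethnicity, other demographics available in both control sources, single vs multiple anomaly, anomaly type (lethal vs non-lethal or grouped organ system), gestational age at diagnosis and twin gestation. Charges will be analyzed by linear regression on log charges.

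Use recruiting site rather than delivery site. Propensity weighting and separate comparisons with prospective and retrospective controls should be labeled as sensitivity analyses only. The latter are weak: power is 30%, 50% or 73% with 50, 100 or 200 controls in a source.

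**Cost.** SAP wording and some coding. Recruitment site is already tracked (6.3). Anomaly detail, ultrasound dates and twin gestation are baseline items that record review can supply (4.3). The anomaly grouping must be agreed before analysis: 5.3 names lethal versus non-lethal as a subgroup, but neither it nor Appendix A defines the split.

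**Power.** Using SE × sqrt((1 − R²y)/(1 − R²g)), where R²y is the share of log-charge variance and R²g the share of group membership that the covariates explain:

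| Assumption | Power |
|---|---|
| Unadjusted | 83.4% |
| Site only, 25-point gap (R²g 0.065), site explaining no charge variance | 80.9% |
| R²y 0.10, R²g 0.10 / 0.20 | 83.4% / 78.9% |
| R²y 0.30, R²g 0.10 / 0.20 | 91.4% / 88.0% |

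A gain is possible but not assured. In the least favorable of these settings power falls about one point below the stated 80%.
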